2. LIST OF ABBREVIATIONS AND DEFINITION OF TERMS

AASLD	American Association for the Study of Liver Diseases
AR	Adverse drug reaction
AE	Adverse event
AFP	Alfa fetal protein
ALT	Alanine aminotransferase
AST	Aspartate aminotransferase
C-G	Cockcroft-Gault
CHB	Chronic Hepatitis B
CrCl	Creatinine clearance
eCRF	Electronic case record form
CRO	Contract research organization
DNA	Deoxyribonucleic acid
DSPH	Drug Safety & Public Health
EASL	European Association for the Study of the Liver
EMA	European Medicines Agency
EudraCT	European Clinical Trials database
FDA	(United States) Food and Drug Administration
GCP	Good Clinical Practices
GEP	Good Epidemiological Practices (guidelines for)
GSI	Gilead Sciences, Inc.
HBV	Hepatitis B Virus
HCC	Hepatocellular carcinoma
HCV	Hepatitis C Virus
HDV	Hepatitis Delta Virus
HIV	Human immunodeficiency virus
IQR	Inter quartile ranges
IV	Intravenous
IFN	Interferon
LLQ	Lower limit of quantification
MDRD	Modification of Diet in Renal Disease
NIS	Non-interventional study
PEG	Polyethylene glycol
SAE	Serious adverse event
SD	Standard Deviation
SmPC	Summary of product characteristics
TDF	tenofovir disoproxil (as fumarate)

Cohort	Group of people characterized by a common experience (e.g., occurrence of a specified disease, exposure to a given medication)	
Cases	Group of individuals with the condition of interest	
Controls	Group of individuals without the condition of interest but are otherwise similar to cases, or unexposed to or not treated with the agent of interest	
Exposure	A variable whose effect is of interest and is being studied	
Outcome	An event (such as disease occurrence or death) that is studied in relation to exposure	
Confounder	Extraneous factor that accounts for a difference in disease frequency between the exposure groups; associated factors serving as surrogates for these factors are also commonly called confounders	
Confounding by indication	A patient characteristic that is related to the outcome of interest and which influences treatment choice (exposure)	
Effect modifier	If an effect measure varies within categories or levels of a variable, that variable is described as an effect-measure modifier	
Bias	Systemic error in the design, conduct or analysis of a study that results in a mistaken estimate	
Prevalence	Proportion of persons with the exposure/outcome at a specific point in time	
Rate	A measure of event occurrence, calculated by dividing the total number of events by the total amount of person-time within an exposure category	
Risk	The proportion of a fixed cohort in which an outcome occurs during a specified period of time	
Relative Risk (RR)	A general term that can refer to the ratio of 2 risks or the ratio of 2 rates	
Odds	The ratio of the probability that an event will happen to the probability that it will not happen	
Internal validity	Whether or not the study provides an unbiased estimate of what it claims to estimate	
External validity (generalizability)	Whether or not the results from the study can be generalized to other populations	

4. PROTOCOL SYNOPSIS/ABSTRACT

Gilead Sciences GmbH [name] Germany

Study Title:	VIR-Life : Prospective assessment of the real-life treatment outcomes of six years of Viread [®] in CHB following-up on the German Multicenter Non-Interventional Study GEMINIS		
Rationale and Background:	The efficacy and safety of TDF is well established by data from randomized controlled trials (RCTs) in various patient populations, such as the Gilead sponsored studies GS-US-174-102 and GS-US-174-103 in treatment naïve patients, or GS-US-174-106, GS-US-174-115 and GS-US-174-121 in patients previously treated with oral antivirals.		
	Clinical studies, such as RCT's investigate the efficacy and safety of a drug in predefined populations, therefore providing high internal validity. Data generated in real-life settings allows for investigating the external validity of the effects seen in RCTs. Thus the real-life treatment outcomes of the drug can be investigated in observational studies such as non-interventional studies (NIS).		
	The real-life treatment outcomes of Viread [®] have been investigated in GEMINIS for a period of 3 years. VIR-Life is the roll-over non- interventional study from GEMINIS to allow the prospective evaluation of the real-life treatment outcomes for additional 3 years.		
Research Question and	The primary objective of this study is as follows:		
Objectives:	• Prospectively describe the virological response, defined as HBV- DNA concentration, during 6 years Viread [®] treatment for CHB in a real life setting.		
	The secondary objectives of this study are to evaluate the:		
	• Safety and tolerability of 6 years of Viread [®] in CHB in a real life setting		
	 Adverse drug reactions (AR) (unrelated Adverse Events (AEs) will also be listed in the report) 		
	• Renal safety		
	Estimated creatinine clearance (eCrCl)		
	Serum creatinine level		

Serum phosphorus level			
	• Histological improvement of the liver		
Study Design:	Prospective non-interventional multicenter cohort post-authorization safety study (single treatment case series)		
Population / Setting:	Roll-over study in adult, HBV-mono-infected CHB patients who started CHB treatment with Viread [®] in GEMINIS		
Duration of Study:	3 years after rolling over from GEMINIS		
Variables: Documentation of routine visits at month 48, 60 and 72, covering following parameters (if available):			
	 Weight Serum HBV-DNA concentration HBeAg, anti-HBe; HBsAg, antiHBs ALT-level Serum creatinine, eCrCL, serum phosphorus Albumine, Bilirubine, Thrombocytes, Prothrombine time (i.e. Quick value) Liver histology staging, transient elastography HCC development Co-morbidities, Incident co-infections with HIV, HCV or HDV Amount of alcohol consumption Adverse events Special Situations; pregnancies, medication error, abuse, misuse, overdose, lack of effect, adverse events in infants following exposure from breastfeeding and adverse events associated with product complaints Dosing of Viread[®] Reason for discontinuation of Viread[®], if applicable 		
Data Sources:	Collection of routine visit data via eCRF		
Study Size:	250 patients		
Data Analysis:	 Descriptive analysis: Categorical and ordinal variables will be described by sample size and the frequency of each modality (over the total number of responses). Quantitative variables will be described by the number of responses, mean, standard deviation, minimum, maximum & madian of all available data. 		

	• Inferential analysis:
	When deemed necessary, sub-group comparisons and/or between time point comparisons may be implemented.
	• Multivariate analysis:
	The potential dependence of treatment outcome frequency with other outcome variables or baseline characteristics will be investigated through methods of multivariate analysis.
Milestones:	Start of data collection : approx. May 2013
	End of Data collection: December 2016
	Interim analysis: planned for Sept. 2014 (year 4 data) and Sept. 2015 (year 5 data)
	Final Study report: April 2017 (year 6 data)
	Publication: submission in Q2-3 2017

This study will be conducted in accordance with the guidelines of Good Pharmacoepidemiology Practices (GPPs), Heads of Medicines Agencies (HMA) and Good Pharmacovigilance Practices (GVP) including archiving of essential documents.

5. AMENDMENTS AND UPDATES

Amendment or update number	Date	Section of study protocol	Amendment or update	Reason
none				

6. MILESTONES

Milestone	Planned date
Start of data collection	Approx. May 2013
End of data collection	December 2016
Year four interim analysis	September 2014
Year five interim analysis	September 2015
Registration in the EU PAS register	before start of data entry into the eCRF
Final report of study results	April 2017
Submission of study report to authority	Q2-3 2017

7. RATIONALE AND BACKGROUND

7.1. Background and medical relevance of chronic hepatitis B (CHB)

Chronic hepatitis B is a serious global health care problem and a major cause of chronic liver disease, cirrhosis, and hepatocellular carcinoma (HCC). Worldwide, approximately 350–400 million people have developed chronic hepatitis B and approximately 1 million people die annually of complications of chronic hepatitis B [1].

Following acute hepatitis B infection, approximately 5% of adults and up to 90% of infected babies fail to produce an immune response adequate to clear the infection; these individuals become chronic carriers of the virus [2–4].

Chronic hepatitis B has a broad clinical spectrum, ranging from asymptomatic, slowly progressive illness to severe, and more rapidly progressive liver disease. Chronic hepatitis B may remain quiescent for many years. However, 15–40% of patients with chronic hepatitis B will eventually develop serious liver disease and complications, such as cirrhosis, hepatic decompensation, and HCC [1]. In patients with chronic hepatitis B, the annual probability of developing cirrhosis varies from 0.1% to 1.0%, depending on the duration of HBV replication, the severity of disease, and the presence of concomitant risk factors. Worldwide, chronic viral Hepatitis B contributes to 30 % of all cases of liver cirrhosis and 53% of the cases of HCC [5].

Asian studies suggest that the level of viral replication is strongly correlated with disease progression towards cirrhosis and HCC [6,7] and that effective suppression of viral replication can alter the course of the disease and decrease morbidity, even in advanced liver disease [8]. However, the clinical benefit is lost if viral replication resumes as a result of emerging resistance mutations [8,9].

Although the hepatitis B virus is distributed worldwide, there are hyper endemic areas (>50% of the population anti-HBc positive) in Asia, the South Pacific, in sub-Sahara Africa, in South America and the Middle East. Areas with intermediate prevalence (10-15%) are the Mediterranean Region and Eastern Europe [2].

Germany is among the countries with low prevalence of chronic HBV infection. [10,11]. In the 1998 national health survey, the sero-prevalence of hepatitis B surface antigen in Germany was 0.6% [12]. Population migration is changing the prevalence and incidence of the HBV disease in several low endemic countries in Europe [2,13,14]. In Germany, especially during the 1960s economic boom, foreign workers were recruited under government programmes to work in Germany [15]. The majority of these workers and their families who migrated to Germany originate from areas with intermediate HBV prevalence, e.g. Turkey and Italy. In the 1990s, people with German descent from the countries of the former Soviet Union and Warsaw Pact States were allowed to repatriate to Germany under a special programme [16]. The effect of migration on the CHB prevalence in Germany is also reflected in a cross sectional study with 1535 patients with replicative chronic HBV infection (HBV DNA >10⁴ copies/ml) living in Germany[13]. It was demonstrated that only 31.7% of the patients were originally from Germany while 68.3% of the CHB patients were born in other countries, mainly Turkey (22.4%), countries of the former Soviet Union (11.2%) and South-East Asia (9.4%) [13].

A safe and effective vaccination against HBV can support the prevention of an infection. It offers, however, no option of cure for those 350-400 million people worldwide, who are estimated to be chronically infected [1].

A significant proportion of chronic HBV carriers are infected with a variant that produces little to no hepatitis B e antigen (HBeAg) (commonly refered to as HBeAg-negative disease). Community based studies from different parts of the world have shown that the prevalence of HBeAg-negative disease can exceed 70%. For example, in Italy over the past decades, 90% of the patients with CHB were reported as HBeAg-negative [17]. The prevalence of HBeAg-negative CHB appears to vary geographically, with the greatest prevalence in the Mediterranean region (33%), followed by 15% in the Asia Pacific region and 14% in the United States and Northern Europe. Overall, the prevalence of HBeAg-negative CHB is apparently increasing worldwide [18].

This HBeAg-negative form of CHB is distributed worldwide with an increasing incidence and is becoming the predominant type of CHB in several countries, particularly in Europe. In patients who are infected with genotypes B and D, development of HBeAgnegative CHB occurs much more frequently than in patients infected with the other HBV genotypes, particularly genotypes A and C [19]. HBeAg-negative CHB disease is typically seen in older patients and develops during the course of HBeAg-positive HBV infection either during or after HBeAg loss or seroconversion [20]. Patients may have persistent or intermittent increases in ALT levels with lower levels of replicating virus as measured by serum HBV DNA. Frequently patients who present with HBeAg-negative disease have more advanced disease. Development of cirrhosis is frequent, associated with increased morbidity and mortality; if left untreated, 15% to 20% of patients will develop liver decompensation within 5 years, 15% will die within 5 years of any cause, and 15% to 30% will die of liver disease. Therefore, the need for effective treatment of HBeAg-negative CHB patients is obvious [21].

The goal of therapy for hepatitis B is to improve quality of life, morbidity and mortality by preventing progression of the disease to cirrhosis, decompensated cirrhosis, end-stage liver disease, HCC and death [2–4]. This goal can be achieved if HBV replication can be suppressed in a sustained manner, the accompanying reduction in histological activity of chronic hepatitis lessening the risk of cirrhosis and decreasing the risk of HCC in non-cirrhotic patients and probably also, but to a lesser extent, in cirrhotic patients [2–4]. However, HBV infection cannot be completely eradicated due to persistence of covalently closed circular DNA (cccDNA) in the nucleus of infected hepatocytes [22].

According to current European and German clinical practice guidelines for the management of CHB [2,4] the indications for treatment are generally the same for both HBeAg-positive and HBeAg-negative CHB. It is based mainly on the combination of three criteria:

- Serum HBV DNA levels
- Serum ALT levels
- Severity of liver disease

According to the EASL Clinical Practice Guidelines [2], Patients should be considered for treatment when they have "HBV DNA levels above 2000 IU/ml, serum ALT levels above the upper limit of normal (ULN) and severity of liver disease assessed by liver biopsy (or non-invasive markers once validated in HBV-infected patients) showing moderate to severe active necroinflammation and/or at least moderate fibrosis using a standardised scoring system". In patients who fulfill the above criteria for HBV DNA and histological severity of liver disease, treatment may be initiated even if ALT levels are normal.

Indications for treatment may also take into account age, health status, family history of HCC or cirrhosis and extrahepatic manifestations.

In the following special groups of patients, treatment is highly recommended:

- Patients with compensated cirrhosis with detectable HBV-DNA should be considered for treatment even if ALT levels are normal and/or HBV-DNA levels are below 2000 IU/ml [4].
- Patients with decompensated cirrhosis and detectable HBV DNA require urgent antiviral treatment.

The following groups of patients usually do not require treatment, however, treatment indication may be considered under certain circumstances:

- Immunotolerant patients: most patients under 30 years of age with persistently normal ALT levels and a high HBV-DNA level, without any suspicion of liver disease and without a family history of HCC or cirrhosis do not require immediate liver biopsy or therapy. Follow-up is mandatory. Consider liver biopsy or even therapy in such patients over 30 years of age and/or with a family history of HCC or cirrhosis
- HBeAg-negative patients with persistently normal ALT levels and HBV DNA levels above 2000 but below 20,000 IU/ml, without any evidence of liver disease, do not require immediate liver biopsy or therapy.

Currently, there are two distinct therapeutic principles for the treatment of chronic hepatitis B: Firstly, (Peg)-Interferon alpha (IFN) for subcutaneous injection, and secondly, orally administered HBV-polymerase inhibitors with direct antiviral activity. These are, in order of marketing approval date, Lamivudine (LAM), Adefovir dipivoxil (ADV), Entecavir (ETV), Telbivudine (LdT) and Tenofovir disoproxil (as fumarate, TDF).

Interferon alpha offers only a moderate antiviral effect, however the theoretical advantages are the absence of resistance and the potential immune modulating effect. Frequent side effects and the generally poor tolerance limit the number of potential patients suitable for treatment with IFN. IFN is contra-indicated in patients with decompensated liver disease [2–4].

Entecavir and TDF, both potent HBV inhibitors with a high barrier to resistance, are recommended as fist-line treatment in national German as well as international treatment guidelines [2–4]. According to the EASL Guidelines, the other three nucleos(t)ide analogues (NAs) should only be used in the treatment of CHB if more potent drugs with high barrier to resistance are not available or appropriate [2]. As of Lamivudine, the EMA has restricted the indication for Zeffix[®] (LAM) in 2010. Initiation of lamivudine treatment should now "only be considered when the use of an alternative antiviral agent with a higher genetic barrier is not available or appropriate" [23]

When viral resistance against an administered medication emerges, the German national guidelines [4] published in 2011, as well as the European Guidelines (EASL) published in 2012 [2] recommend switching to a non-cross-resistant second drug or adding it on top. As the choice of drugs with complementary resistance profiles is limited, the therapeutic choice should be driven by an effort to effectively avoid any development of resistance by using the most potent agents with the highest barrier to resistance in the initial first-line therapy of CHB [2,4].

7.2. Tenofovir Disoproxil Fumarate (Tenofovir DF)

Tenofovir disoproxil (245 mg, as fumarate; TDF, Viread[®]) is an oral prodrug of Tenofovir, a acyclic nucleotide (nucleoside monophosphate) analogue.

Tenofovir diphosphate, the activated (phosporylated) compound, is a potent and selective inhibitor of both human immunodeficiency virus type 1 (HIV-1) reverse transcriptase and hepatitis B virus (HBV) polymerase, inhibiting viral polymerases by direct competitive binding with the natural deoxyribonucleotide substrate (i.e., deoxyadenosine triphosphate, dATP) and, after incorporation into DNA, by DNA chain termination.

Tenofovir DF is the active ingredient in Viread®, which is approved as a once-daily, film-coated tablet for the treatment of HIV-1 infection in more than 50 countries worldwide. Tenofovir DF was approved in 2008 for the treatment of chronic hepatitis B in the European Union, Turkey, New Zealand, Australia, Canada, and in the United States.

Efficacy and safety of TDF in currently being investigated in mono-infected HBV patients in the open label follow up of the two phase III pivotal RCTs (GS-US-174-102 and GS-US-174-103). The first 48 weeks compared in a double blind randomized controlled design the efficacy and safety of TDF vs. Adefovirdipivoxil 10 mg QD in CHB. TDF showed superior anti-HBV activity compared to Adefovir both in HBeAg negative and positive patients [24].

Experience in patients with compensated liver disease at 48 weeks (studies GS-US-174-0102 and GS-US-174-0103)

At week 48, viral suppression occurred in more HBeAg-negative patients receiving TDF than patients receiving Adefovir (93% vs. 63%, P<0.001) and in more HBeAg-positive patients receiving TDF than patients receiving Adefovir (76% vs. 13%, P<0.001). Significantly more HBeAg-positive patients treated with TDF than those treated with Adefovir had normalized alanine aminotransferase levels (68% vs. 54%, P=0.03) and loss of hepatitis B surface antigen (3% vs. 0%, P=0.02). At week 48, amino acid substitutions within HBV DNA polymerase associated with phenotypic resistance to TDF or other drugs to treat HBV infection had not developed in any of the patients. TDF produced a similar HBV DNA response in patients who had previously received Lamivudine and in those who had not. The safety profile was similar for the two treatments in both studies [24,25].

Experience beyond 48 weeks

In studies GS-US-174-0102 and GS-US-174-0103, after receiving double-blind treatment for 48 weeks (either TDF 245 mg or Adefovir 10 mg), patients rolled over with no interruption in treatment to open-label TDF. In studies GS-US-174-0102 and GS-US-174-0103, 81% and 70% of patients continued in the study through to 240 weeks, respectively. At weeks 96, 144, 192 and 240, viral suppression, biochemical and serological responses were maintained with continued TDF treatment [25,26].

Paired baseline and week 240 liver biopsy data were available for 331/489 patients who remained in studies GS-US-174-0102 and GS-US-174-0103 (see Table 5 below). Ninety-five percent (225/237) of patients without cirrhosis at baseline and 99% (93/94) of patients with cirrhosis at baseline had either no change or an improvement in fibrosis (Ishak fibrosis score). Of the 94 patients with cirrhosis at baseline (Ishak fibrosis score 5-6), 26% (24) experienced no change in Ishak fibrosis score and 72% (68) experienced regression of cirrhosis by week 240 with a reduction in Ishak fibrosis score of at least 2 points [25,27].

Clinical resistance

426 HBeAg negative (GS-US-174-0102, n = 250) and HBeAg positive (GS-US-174-0103,

n = 176) patients were evaluated for genotypic changes in HBV polymerase from baseline. Genotypic evaluations performed on all patients initially randomised to the TDF arm (i.e. excluding patients who received double-blind Adefovir and then switched to open-label TDF) with HBV DNA > 400 copies/ml at week 48 (n = 39), week 96 (n = 24), week 144

(n = 6), week 192 (n = 5) and week 240 (n = 4) on TDF monotherapy, showed that no mutations associated with TDF resistance have developed [25].

7.3. GEMINIS

The GEMINIS Study

GEMINIS was the first prospective non-interventional observational study on the real-life treatment outcomes and the patterns of use of three years of Viread[®] in Germany. The study recruited adult patients with HBV mono-infection. At inclusion, patients were TDF-naïve, however, previous treatment for CHB was accepted. Documentation and treatment decisions were at the sole discretion of the participating physician.

Baseline Characteristics

35 centers (20% hospitals, 80% office-based) enrolled 400 CHB patients from May 2009 - May 2010. Most frequent countries of birth were: 31% Germany, 19% Turkey, 8.5% Russia, 6.5% Vietnam, 3% Poland. The main reason for using Viread[®] was persistent viremia (25%) or virologic relapse despite previous treatment (10%). 90% initiated TDF monotherapy. Additional baseline characteristic are summarized in table 1.

Age • mean (+/-SD) [years]	44.5 (+/- 13.8)
• 18-65; > 65 [years]	91%; 9%
Male	69%
Caucasian	76%
ALT > ULN*	55%
HBeAg-negative	69%
Serum HBV DNA[IU/ml]Median (IQR)• entire group $(N=400)$ • naïve patients $(n=183)$ • experienced patients $(n=217)$	40-4.0x10 ⁵) 8x10 ³ - 6.8x10 ⁶) 20 - 2.0x10 ⁴)
Treatment naïve	46%
Biopsy done (fibrosis score $\geq 2^{**}$)	14% (37%)
Elastography data (advanced fibrosis***)	17% (22%)
Cirrhosis***	11%
TDF monotherapy	92%
*ULN: Male \leq 43 IU/L, female \leq 34 IU/L; by physician	**by Desmet-Scheuer or Metavir; *** as defined

Table 1: Baseline patient characteristics

GEMINIS – Results after 24 month of follow up

Viread[®] was primarily used as monotherapy. After 24 month of follow up, HBV replication was suppressed through 24 months in the majority of treatment naïve and experienced patients, regardless of pre-treatment status. HBeAg-loss/-seroconversion was documented in 23 % and 19 % of HBeAg+ patients, respectively. A 5.1 % cumulative probability for HBsAg-loss in HBeAg+ patients was observed. This rate is comparable to the 96 week result of TDF registration study 103 [24]. Two patients HBeAg-negative at baseline lost HBsAg. The overall safety profile of Viread[®], including renal safety, was very favorable in this real-life setting (Table 2) [28].

	Treatment- naïve (n=183)	Treatment - experienced (n=217)		
HBV-DNA < 169 IU/ml • HBeAg-positive • HBeAg-negative • prior LAM+ADV • prior ETV	88 % 94 % NA NA	94 % 97 % 100 % 96 %		
HBV-DNA < 69 IU/ml • HBeAg-positive • HBeAg-negative • prior LAM+ADV • prior ETV	81 % 80 % NA NA	84 % 90 % 89 % 92 %		
ALT < ULN* HBeAg-loss	71%	77 %		
HBeAg-seroconversion HBsAg-loss**(HBeAg+ at baseline)	19 % 5.1 %			
HBsAg-loss (HBeAg- at baseline) $2/226$ with documented HBsAg*ULN: Male ≤ 43 IU/L, female ≤ 34 IU/L; ** Kaplan Meier Estimate (Cumulative probability in patients with documented HBsAg)				

Table 2: 2 years virological, serological and biochemical results[28]

Tuble of of cume clearance aaring fonon ap	Table 3:	Creatine-clearance	during	follow-up
--	----------	---------------------------	--------	-----------

Estimated CrCl (Cockcroft-Gault)	Baseline (n = 361)	Month 6 (n = 299)	Month 12 (n = 289)	Month 24 (n = 255)
Mean [ml/min] (SD)	106.9 (31.6)	105.9 (33.8)	104.7 (31.7)	102.2 (31.3)
Mean change [ml/min] (SD)		-1.4 (16.1)	-3.2 (16.2)	-3.4 (15.4)

8. **RESEARCH QUESTION AND OBJECTIVES**

Clinical studies, such as RCT's investigate the efficacy and safety of a drug in predefined populations, therefore providing high internal validity. Data generated in real-life settings allows for investigating the external validity of the effects seen in RCTs. Thus the real-life treatment outcomes of the drug can be investigated in observational studies such as non-interventional studies (NIS).

The real-life treatment outcomes of Viread[®] have been investigated in GEMINIS for a period of 3 years. VIR-Life is the roll-over non-interventional study from GEMINIS to allow for the continued prospective evaluation of the real-life treatment outcomes for additional 3 years.

The primary objective of this study is as follows:

• Prospectively describe the virological response, defined as HBV-DNA concentration, during 6 years Viread[®] treatment for CHB in a real life setting.

The secondary objectives of this study are to evaluate the:

- To describe the safety and tolerability of 6 years of Viread[®] in CHB in a real life setting, and report the following:
 - Adverse drug reactions (ADR) (unrelated Adverse Events (AEs) will also be listed in the report)
 - Renal safety
 - Estimated creatinine clearance (eCrCl)
 - Serum creatinine level
 - Serum phosphorus level
- Histological improvement of the liver

9. **RESEARCH METHODS**

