9.4. Data Sources

The conduct of a non-interventional study (NIS) requires, according to definition of a "non-interventional study" in terms of Guideline on good pharmacovigilance practices (GVP) – Module VIII (Rev 1), that the protocol does not stipulate or dictate on the diagnosis, therapeutic decisions and follow-up of the individual patient. The study only observes and collects the use of a drug and the corresponding clinical outcome by the treating physician in the specific indication.

Clinical data is collected from the physician's documentation of the patient's visit in patient medical records that is closest to the documentation time point (month 48, 60 and 72), each +/- 3 months. Primary data sources are electronic medical records, where available or paper records at the participating sites. This data will then be manually transcribed by the investigator into electronic case record form (eCRF).

In this non-interventional follow up study, the following findings are of special interest and information will be collected accordingly:

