9.4.1. Baseline

VIR-life is the extended follow up of GEMINIS. Therefore, VIR-life baseline data is the data that was collected at GEMINS baseline.

9.4.2. During VIR-Life follow up and at end of follow up (month 48, 60 and 72):

- HBV- virology and serology parameters
- Biochemical serum-parameters
 - ALT
- Renal safety parameters
 - Serum creatinine, eCrCl, serum phosphorus
- Liver synthesis parameters
 - Albumin, bilirubin, thrombocytes, prothrombin time (Quick-Value)
- Liver histology, elastography, incident HCC
- Co-morbidities, Co-infections, alcohol consumption
- Adverse events
- Special Situations; pregnancies, medication error, abuse, misuse, overdose, lack of effect, adverse events in infants following breastfeeding, and adverse events associated with product complaints
- Dosing of Viread[®]
- Combination therapy
- Reason for discontinuation of Viread[®], if applicable

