9.5. Study Size

The planned study size is 250 patients. This number is pre-specified by the number of eligible patients to be rolled over from GEMINIS in the participating 25 study sites.

To maximize the possible sample size, all eligible patients in the participating sites shall be rolled over into the study.

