9.9. Limitations of the research methods

In a non-interventional study all decisions on the management of the patient are made solely by the treating physician. This also includes the frequency of the evaluation of lab values and other collected variables. Documentation of study variables must not be made obligatory. Missing data of unpredictable extent can occur.

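### Histological improvement is a secondary objective but can only be described in a small, physician-selected subset, and the visit-window rule may lose some of the few paired results

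*Protocol*

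**What the plan says.** The synopsis and Section 8 both list "Histological improvement of the liver" among the secondary objectives. Neither says how improvement is judged or in which patients.

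The starting point is fixed in Section 9.4.1: "VIR-life baseline data is the data that was collected at GEMINS baseline". Table 1 in Section 7.3 shows what that baseline holds. GEMINIS "enrolled 400 CHB patients from May 2009 - May 2010". The row beginning "Biopsy done (fibrosis score" gives 14%, with 37% of those at a score of 2 or more, staged by either of two scoring systems. Elastography data existed for 17%, with 22% of those showing advanced fibrosis.

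Section 9.3 places biopsy results and Fibroscan under one heading, liver histology and HCC. Section 9.4.2 lists histology, elastography and incident HCC together among the follow-up items. Section 9.4 says that clinical data come from the visit "closest to the documentation time point (month 48, 60 and 72), each +/- 3 months". It makes no exception for procedures that are done rarely.

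Section 9.9 adds: "Documentation of study variables must not be made obligatory". On size, Section 9.5 states: "The planned study size is 250 patients". It explains: "This number is pre-specified by the number of eligible patients to be rolled over from GEMINIS in the participating 25 study sites".

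**The concern.** A patient without a baseline biopsy cannot show histological improvement, and a baseline that lies years in the past cannot be filled in. Section 7.3 shows that about six patients in seven had no baseline biopsy. Among the rest, a second biopsy depends on the treating physician's decision, so the pairs will be few and selected for clinical reasons that the study does not control. The objective, as worded, suggests a statement about the cohort that these data cannot carry.

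The capture rule adds a second difficulty. Laboratory values recur at most visits, so taking the visit nearest each time point loses little. A biopsy may occur once in three years. If a site transcribes only what was done at the visit nearest month 48, 60 or 72, a result from between the windows can be missed. No later analysis decision recovers a result that was never entered, which is why this belongs in the protocol rather than the SAP.

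**Working it through.** **Inputs.** From the protocol: GEMINIS cohort 400, biopsy 14%, elastography 17%, score of 2 or more in 37% of biopsies, advanced fibrosis in 22% of scans (Section 7.3, Table 1); planned size 250 (Section 9.5). Not in the protocol: the baseline biopsy and scan rates among roll-over patients, and the follow-up rate *f*. Both are assumed below. Section 9.5 gives no power or precision calculation, so there is no plan figure to reproduce.

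**Step 1: GEMINIS baseline readings.** Biopsy: 0.14 × 400 = 56 (54 to 58, allowing for rounding of the 14%). Elastography: 0.17 × 400 = 68.

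**Step 2: carried over to VIR-Life (assuming the same rates).**
- Biopsy: 0.14 × 250 = 35, of whom 0.37 × 35 = 12.95, about 13, scored 2 or more.
- Elastography: 0.17 × 250 = 42.5, about 43, of whom 0.22 × 42.5 = 9.35, about 9, had advanced fibrosis.
- Either method: from 17% (full overlap) to 14% + 17% = 31% (no overlap), or about 43 to 78 patients, before any loss at follow-up.

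Without the carry-over assumption, the biopsy ceiling is the 56 GEMINIS patients themselves. Even if all of them rolled over, that is 56/250 = 22%.

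**Step 3: biopsy pairs.** Pairs = 35 × *f*. The interval is the exact (Clopper-Pearson) 95% CI if about half of the pairs improved, used only to illustrate precision.

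| Assumed *f* | Pairs | Share of 250 | Example | 95% CI |
|---|---|---|---|---|
| 5% | 1.75, about 2 | 0.7% | 1/2 | 1% to 99% |
| 14% | 4.9, about 5 | 2.0% | 2/5 | 5% to 85% |
| 25% | 8.75, about 9 | 3.5% | 4/9 | 14% to 79% |
| 50% | 17.5, about 18 | 7.0% | 9/18 | 26% to 74% |
| 67.7% | 23.7, about 24 | 9.5% | 12/24 | 29% to 71% |
| 100% | 35 | 14% | 17/35 | 31% to 66% |

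The 67.7% row borrows the pairing rate that Section 7.2 reports for the registration studies (331/489). It is a generous scenario for routine care.

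**Step 4: elastography pairs.** 42.5 × *f*: about 2 at 5% and about 21 at 50%. These are not histology and should not be pooled with biopsy.

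**Step 5: the capture rule.** Months 48, 60 and 72, each within 3 months, give windows of 45–51, 57–63 and 69–75. Section 9.4 ties clinical data to the visit nearest each point. The heading of Section 9.4.2 speaks of data during follow-up but names the same three months. Neither section says what to do with a biopsy dated, for example, month 54. One site could enter it at month 60 from the patient's record; another could leave it out. Both would be following the text.

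**The case against.** The strongest reply is that this is a descriptive study whose size is set by the roll-over, with no power claim. Items are collected if available, and Section 9.9 warns that missing data of unpredictable extent can occur. A small paired subset can be described with its denominator, and Section 9.7 requires the number of responses. This stands, and it rules out saying that the objective cannot be addressed at all. It does not answer the point that the wording suggests a cohort-level finding. Section 9.9 does not mention histology, and the 14% was known when the objective was written.

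A reader might go further in three ways that the protocol does not support.

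- *Results between windows are never captured.* Section 9.4 puts the 3 months on the visit, not on the date of the biopsy, and the month-60 record may mention a biopsy from month 54. Incident HCC sits in the same bullet of Section 9.4.2 and makes little sense as a single-visit snapshot. The text is ambiguous, not exclusionary.
- *About half of all results are lost.* The windows span 18 of the 39 months from 36 to 75, but turning that into a loss assumes both the strict reading and random timing. The protocol supports neither.
- *Section 9.7 plans an unpaired comparison of stage distributions.* It does not. It allows comparisons between time points, and the pairing rule is ordinary SAP content. Table 3 of Section 7.3 points towards within-patient change: the mean change in creatinine clearance at month 24 is −3.4, while the difference of the visit means is 102.2 − 106.9 = −4.7.

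It is also fair to object that the 14% describes all 400 GEMINIS patients and that the re-biopsy rate has no anchor in the protocol. Both are therefore treated as assumptions.

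**Conclusion.** The point holds in limited form. Histological improvement can be described in a small, physician-selected subset; it cannot be evaluated for the cohort. If the GEMINIS baseline rates apply to the roll-over patients, biopsy pairs number at most about 35 of 250, and about 2 to 18 at assumed re-biopsy rates of 5% to 50%. The conclusion does not turn on the re-biopsy rate: with every baseline-biopsied patient re-biopsied, the illustrative interval still runs from 31% to 66%, and those patients are 14% of the cohort. Nor does it turn on the carry-over rate, since no more than about 56 patients, 22% of 250, could have a baseline biopsy.

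Separately, Section 9.4 leaves it unclear whether biopsies and scans done between windows are recorded. How many pairs this would cost cannot be estimated from the protocol, but with so few expected, each one matters. This concerns a secondary objective and does not touch the primary one.

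**What to change.** 1. In Section 9.4, exempt biopsy and elastography from the visit window. Record every result since GEMINIS month 36, with its date, method and score, in a repeatable eCRF form.
2. In Section 8 and the synopsis, reword the objective: describe within-patient change in fibrosis among patients with paired assessments by the same method. State that biopsy and elastography are reported separately and that the number of pairs is shown.

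The cost is a little more data entry and a more modest objective. No procedure is added, only results from routine care are recorded, and the study stays non-interventional.
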